4.3.1 Antiemetic Premedications

Antiemetic premedications should not be routinely administered prior to dosing of study drug.

4.3.2 Dose Delay Criteria

Dose delay criteria apply for all drug-related adverse events. Nivolumab must be delayed until treatment can resume (see [Section 4.3.4](#)).

Nivolumab administration should be delayed for the following:

- Any Grade ≥ 2 non-skin, drug-related adverse event, with the following exceptions:
 - Grade 2 drug-related fatigue or laboratory abnormalities do not require a treatment delay.
- Any Grade 3 skin, drug-related adverse event.
- Any Grade 3 drug-related laboratory abnormality, with the following exceptions for lymphopenia, leukopenia, AST, ALT, or total bilirubin:
 - Grade 3 lymphopenia or leukopenia does not require dose delay.
If a subject has a baseline AST, ALT or total bilirubin that is within normal limits, delay dosing for drug-related Grade ≥ 2 toxicity.
If a subject has baseline AST, ALT, or total bilirubin within the Grade 1 toxicity range, delay dosing for drug-related Grade ≥ 3 toxicity.
- Any adverse event, laboratory abnormality, or intercurrent illness which, in the judgment of the investigator, warrants delaying the dose of study medication.

[REDACTED]

- [REDACTED]
- [REDACTED]
- [REDACTED]
- [REDACTED]
- [REDACTED]
- [REDACTED]
- [REDACTED]
- [REDACTED]

[REDACTED]

4.3.3 Dose Modifications

Dose reductions and escalations of nivolumab are not permitted.

4.3.4 Criteria to Resume Nivolumab Dosing

Subjects may resume treatment with nivolumab (BMS-936558) when the drug-related AE(s) resolve(s) to Grade \leq 1 or baseline, with the following exceptions:

- Subjects may resume treatment in the presence of Grade 2 fatigue.
- Subjects who have not experienced a Grade 3 drug-related skin AE may resume treatment in the presence of Grade 2 skin toxicity.
- Subjects with baseline AST/ALT or total bilirubin in the Grade 1 toxicity range who require dose delays for reasons other than a 2-grade shift in AST/ALT or total bilirubin may resume treatment in the presence of Grade 2 AST/ALT OR total bilirubin.
- Subjects with combined Grade 2 AST/ALT AND total bilirubin values meeting discontinuation parameters (Section 4.3.5) should have treatment permanently discontinued.
- Drug-related pulmonary toxicity, diarrhea, colitis or nephritis must have resolved to baseline before treatment is resumed.
- Drug-related endocrinopathies adequately controlled with only physiologic hormone replacement may resume treatment.

If the criterion to resume treatment is met, the subject should restart treatment at the next scheduled time point per protocol.

If treatment is delayed $>$ 6 weeks from the previous dose, the subject must be permanently discontinued from study therapy, except as specified in Section 4.3.5.

4.3.5 Treatment Discontinuation Criteria

Nivolumab treatment should be permanently discontinued for the following:

- Any Grade 2 drug-related uveitis or eye pain or blurred vision that does not respond to topical therapy and does not improve to Grade 1 severity within the re-treatment period OR requires systemic treatment.
- Any Grade 3 non-skin, drug-related adverse event lasting $>$ 7 days, with the following exceptions for laboratory abnormalities, drug-related uveitis, pneumonitis, bronchospasm, hypersensitivity reactions, infusion reactions, and endocrinopathies:
 - ◆ Grade 3 drug-related uveitis, pneumonitis, bronchospasm, hypersensitivity reaction, or infusion reaction of any duration requires discontinuation
 - ◆ Grade 3 drug-related endocrinopathies adequately controlled with only physiologic hormone replacement do not require discontinuation
 - ◆ Grade 3 drug-related laboratory abnormalities do not require treatment discontinuation except:

- Grade 3 drug-related thrombocytopenia > 7 days or associated with bleeding requires discontinuation
- Any drug-related liver function test (LFT) abnormality that meets the following criteria require discontinuation:
 - AST or ALT > 5 - 10 x ULN for > 2 weeks
 - AST or ALT > 10 x ULN
 - Total bilirubin > 5x ULN
 - Concurrent AST or ALT > 3x ULN and total bilirubin > 2x ULN
- Any Grade 4 drug-related adverse event or laboratory abnormality, except for the following events which do not require discontinuation:
 - Grade 4 neutropenia ≤ 7 days
 - Grade 4 lymphopenia or leukopenia
 - Isolated Grade 4 electrolyte imbalances/abnormalities that are not associated with clinical sequelae and are corrected with supplementation/appropriate management within 72 hours of their onset
 - Grade 4 amylase or lipase abnormalities that are not associated with symptoms or clinical manifestations, or radiographic signs of pancreatitis. It is recommended to consult with the BMS Medical Monitor for Grade 4 amylase or lipase abnormalities
 - Grade 3 or 4 drug-related endocrinopathy AEs such as adrenal insufficiency, ACTH (Adrenocorticotropic Hormone) deficiency, hyper- or hypothyroidosis, or glucose intolerance, which resolve or are adequately controlled with physiologic hormone replacement (steroids, thyroid hormones) or glucose controlling agents, respectively, may not require discontinuation after discussion with and approval from the BMS Medical Monitor
- Any dosing interruption lasting > 6 weeks from the previous dose, with the following exceptions:
 - Dosing interruptions to allow for prolonged steroid tapers to manage drug-related adverse events are allowed. Prior to re-initiating treatment in a subject with a dosing interruption lasting > 6 weeks from the previous dose, the BMS medical monitor must be consulted. Tumor assessments should continue as per protocol even if dosing is interrupted
 - Dosing interruptions > 6 weeks from the previous dose, that occur for non-drug-related reasons may be allowed if approved by the BMS medical monitor. Prior to re-initiating treatment in a subject with a dosing interruption lasting > 6 weeks from the previous dose, the BMS medical monitor must be consulted. Tumor assessments should continue as per protocol even if dosing is interrupted
- Any adverse event, laboratory abnormality, or intercurrent illness which, in the judgment of the Investigator, presents a substantial clinical risk to the subject with continued nivolumab (BMS-936558) dosing.

- Disease progression (as determined by investigator assessment following the guidelines given in [section 5.4](#)). Treatment beyond progression is allowed in certain instances as described in [Section 4.3.8](#).
- Subject who initiated the preparative regimen for allogeneic SCT or ASCT after the first dose of nivolumab treatment.

4.3.6 Treatment of BMS-936558-Related Infusion Reactions

Since nivolumab contains only human immunoglobulin protein sequences, it is unlikely to be immunogenic and induce infusion or hypersensitivity reactions. However, if such a reaction were to occur, it might manifest with fever, chills, rigors, headache, rash, pruritus, arthralgias, hypotension, hypertension, bronchospasm, or other allergic-like reactions. All Grade 3 or 4 infusion reactions should be reported within 24 hours to the study medical monitor and reported as an SAE if it meets the criteria. Infusion reactions should be graded according to NCI CTCAE (Version 4.0) guidelines.

Treatment recommendations are provided below and may be modified based on local treatment standards and guidelines, as appropriate:

For Grade 1 symptoms: (Mild reaction; infusion interruption not indicated; intervention not indicated).

- Remain at bedside and monitor subject until recovery from symptoms. The following prophylactic premedications are recommended for future infusions: diphenhydramine 50 mg (or equivalent) and/or acetaminophen/paracetamol 325 to 1000 mg at least 30 minutes before additional nivolumab administrations.

For Grade 2 symptoms: (Moderate reaction requires therapy or infusion interruption but responds promptly to symptomatic treatment [eg, antihistamines, non-steroidal anti-inflammatory drugs, narcotics, corticosteroids, bronchodilators, IV fluids]; prophylactic medications indicated for ≤ 24 hours).

Stop the nivolumab infusion, begin an IV infusion of normal saline, and treat the subject with diphenhydramine 50 mg IV (or equivalent) and/or paracetamol 325 to 1000 mg (acetaminophen); remain at bedside and monitor subject until resolution of symptoms. Corticosteroid or bronchodilator therapy may also be administered as appropriate. If the infusion is interrupted, restart the infusion at 50% of the original infusion rate when symptoms resolve; if no further complications ensue after 30 minutes, the rate may be increased to 100% of the original infusion rate. Monitor subject closely. If symptoms recur then no further nivolumab will be administered at that visit. Administer diphenhydramine 50 mg IV, and remain at bedside and monitor the subject until resolution of symptoms. The amount of study drug infused must be recorded on the electronic case report form (eCRF). The following prophylactic premedications are recommended for future infusions: diphenhydramine 50 mg (or equivalent) and/or paracetamol 325 to 1000 mg (acetaminophen) should be administered at least 30 minutes before additional

nivolumab administrations. If necessary, corticosteroids (recommended dose: up to 25 mg of IV hydrocortisone or equivalent) may be used.

For Grade 3 or 4 symptoms: (Severe reaction, Grade 3: prolonged [ie, not rapidly responsive to symptomatic medication and/or brief interruption of infusion]; recurrence of symptoms following initial improvement; hospitalization indicated for other clinical sequelae [eg, renal impairment, pulmonary infiltrates]. Grade 4: Life-threatening; pressor or ventilatory support indicated).

- Immediately discontinue infusion of nivolumab. Begin an IV infusion of normal saline and treat the subject as follows: Recommend bronchodilators, epinephrine 0.2 to 1 mg of a 1:1000 solution for subcutaneous administration or 0.1 to 0.25 mg of a 1:10,000 solution injected slowly for IV administration, and/or diphenhydramine 50 mg IV with methylprednisolone 100 mg IV (or equivalent), as needed. Subject should be monitored until the Investigator is comfortable that the symptoms will not recur. Nivolumab will be permanently discontinued. Investigators should follow their institutional guidelines for the treatment of anaphylaxis. Remain at bedside and monitor subject until recovery of the symptoms. In the case of late-occurring hypersensitivity symptoms (eg, appearance of a localized or generalized pruritis within 1 week after treatment), symptomatic treatment may be given (eg, oral antihistamine, or corticosteroids).

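### A Grade 2 infusion reaction that recurs after restart carries two incompatible consequences: drug withheld for that visit, or nivolumab stopped permanently

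*Protocol*

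**What the plan says.** Protocol section 4.3.6 sets out the handling of infusion reactions by grade. Its opening paragraph says "Infusion reactions should be graded according to NCI CTCAE (Version 4.0) guidelines" and adds "All Grade 3 or 4 infusion reactions should be reported within 24 hours to the study medical monitor".

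For Grade 2, the infusion is stopped and the symptoms are treated. If it was interrupted, the site is to "restart the infusion at 50% of the original infusion rate when symptoms resolve". The next contingency is recurrence: "If symptoms recur then no further nivolumab will be administered at that visit". The paragraph then turns to later cycles: "The following prophylactic premedications are recommended for future infusions". It does not exclude subjects whose symptoms recurred.

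The description that introduces the Grade 3 or 4 instructions lists, under Grade 3, "recurrence of symptoms following initial improvement". The action for those grades includes "Nivolumab will be permanently discontinued".

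Section 4.3.5, which lists the discontinuation criteria, states: "Grade 3 drug-related uveitis, pneumonitis, bronchospasm, hypersensitivity reaction, or infusion reaction of any duration requires discontinuation".

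**The concern.** The Grade 2 instruction and the Grade 3 description cover the same clinical event but lead to different outcomes. A site reading the Grade 2 paragraph would withhold the rest of that infusion and prepare the subject, with premedication, for the next cycle. A site reading the Grade 3 description would stop nivolumab for good and notify the medical monitor within 24 hours.

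The first stake is patient safety: the same subject could be re-exposed at one site and permanently taken off study drug at another, each site relying on protocol text.

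The second is the safety data. The recorded grade feeds the worst-grade adverse event tables (protocol section 8.4.3). The decision to stop feeds the summary of adverse events leading to discontinuation (SAP sections 7.6.3 and 7.10) and the duration-of-treatment analysis (SAP section 7.4.1). The study has one arm and, per SAP section 2.5, no data monitoring committee, so it relies on sites grading and reporting consistently.

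**Working it through.** No arithmetic applies, and the plan gives no figure to reproduce. The check follows one subject through the text.

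1. The subject has a Grade 2 reaction and the infusion is stopped.
2. The symptoms resolve. The Grade 2 paragraph makes this the condition for restarting, so improvement has taken place before any restart.
3. The infusion is restarted at half the original rate and the symptoms return.
4. The event meets the condition of the Grade 2 recurrence sentence. It is also a recurrence after initial improvement, which is listed under Grade 3 without any further severity threshold. By step 2 this is true of every recurrence after a restart, so the overlap is complete.

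The two routes side by side:

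| Item | Grade 2 paragraph of 4.3.6 | Grade 3 wording of 4.3.6, with 4.3.5 |
|---|---|---|
| Grade | 2 | 3 |
| Study drug at this visit | No more given | Infusion discontinued immediately |
| Study drug afterwards | Limit is stated for that visit; premedication for later infusions follows | Permanently discontinued |
| 24-hour notice to the medical monitor | Not required by the Grade 3 or 4 sentence | Required |

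Other sections do not close the gap:

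- Section 4.3.5 has no criterion naming a Grade 2 infusion reaction. For an event left at Grade 2, its relevant route to stopping is the general one based on the investigator's judgement of clinical risk.
- Section 4.3.4 lets dosing resume once a drug-related event has settled to Grade 1 or below, or to baseline. On the Grade 2 reading, a further dose is therefore permitted.
- Section 4.3.5 does not mention recurrence. It takes effect only once the event is called Grade 3, and that depends on the description in 4.3.6.
- Neither section instructs the site to regrade a reaction that recurs, and neither says which paragraph prevails.

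**The case against.** The best defence is that the passages can be read in sequence: stop at that visit, regrade the event against the printed Grade 3 description, then apply section 4.3.5. On this view the Grade 2 sentence is a bedside instruction that is silent on later cycles. The premedication advice is meant for the many Grade 2 subjects who never have a recurrence. The fault is then only a missing cross-reference. The steps in 4.3.6 are also introduced as recommendations that sites may adapt to local standards, which would give 4.3.5 the stronger claim.

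Part of this stands. The Grade 2 sentence does not say that treatment continues; that is inferred from the limit to a single visit and from the advice on later infusions. Section 4.3.5 reaches the case only through the grade. Some subjects would stop under either reading, because the investigator may judge continued dosing too risky.

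It does not remove the conflict. The sequential reading is written nowhere. If every recurrence became Grade 3, the limit to that visit would apply to no one, so a site could reasonably take the sentence to allow a next dose. The local-adaptation clause softens the conflict inside 4.3.6 but is not attached to the criterion in 4.3.5. The referral to CTCAE does not help either, since the protocol's own Grade 3 description is what clashes with the Grade 2 instruction.

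**Conclusion.** The concern holds. The protocol assigns one event two grades and two consequences for study drug.

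For each affected subject the rules diverge completely on whether a next dose is allowed, on the recorded grade and on 24-hour reporting. How many subjects are affected cannot be estimated: the documents give no rate, section 4.3.6 itself regards infusion reactions as unlikely, and only those that are interrupted, resolve, restart and then recur are involved. The number is probably small.

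The planned sample size and the rule of 25 or more responses in 90 treated subjects do not depend on the grade of an infusion reaction. The effect is on subject safety, prompt reporting and the descriptive safety and exposure tables. That is enough to warrant correction, though not to question the primary test.

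The conclusion rests on two readings of the text: that the limit to that visit, followed by advice for later infusions, leaves further dosing open; and that the Grade 3 description means what it says, with no added severity threshold.

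**What to change.** Reconcile the Grade 2 recurrence sentence in section 4.3.6 with the Grade 3 description in that section and with section 4.3.5. The revised text should give a reaction that recurs after restart one grade and one consequence for study drug, make the 24-hour reporting sentence follow that grade, and say whether the advice on later infusions covers these subjects. Which grade and consequence are right is for the sponsor's medical team; this review takes no position.

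The cost is one or two sentences in 4.3.6 and a memo to sites. No new data or procedures are needed.

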4.3.7 Guidelines for Assessment and Management of Tumor Lysis Syndrome

The possibility of tumor lysis syndrome cannot be ruled out for the subjects with lymphoma. Therefore, adequate management such as hydration and/or the use of allopurinol is recommended in the subjects who have risk factor of potential tumor lysis syndrome, for example the subjects with high tumor burden, reflected by high serum LDH levels, or bulky disease, or those with preexisting renal failure.

4.3.8 Treatment Beyond Disease Progression

4.3.8.1 Circumstances in which post-progression treatment is permitted

Subjects meeting progression defined by relapsed disease (after CR) or progressive disease (after PR, SD) per 2007 IWG criteria may continue receiving study medication beyond investigator-assessed progression as long as they meet the following criteria:

- Continue to meet all other study protocol eligibility criteria
- Investigator-assessed clinical benefit, and do not have rapid disease progression
- Stable performance status
- Treatment beyond progression will not delay an imminent intervention to prevent serious complications of disease progression
- Patients will be re-consented with an informed consent document describing any reasonably foreseeable risks or discomfort and other alternative treatment options
- Tolerance of study drug

The decision to continue treatment beyond investigator-assessed progression should be discussed with the BMS Medical Monitor and documented in the study records. The assessment of clinical benefit should take into account whether the subject is clinically deteriorating and unlikely to receive further benefit from continued treatment.

4.3.8.2 Assessment schedule for the subjects with post-progression treatment

The subject should continue to receive monitoring according to the On-Treatment Assessments on [Table 5.1-2](#) except for FDG-PET scans. Radiographic assessment by CT (preferred) or MRI described in the [section 5.4.1](#) and [Table 5.4.1-1](#) are required when subjects continue post-progression treatment. FDG-PET scans are not mandated after investigator-assessed progression.

4.3.8.3 Discontinuation due to further progression

Subjects should discontinue study therapy upon evidence of further progression, defined as an additional 10% or greater increase in tumor burden volume from time of initial progression (including all target lesions and new measurable lesions).

- Further progression is evaluated by a subsequent CT or MRI which is performed at least 8 weeks from previous CT or MRI.
- The tumor burden volume from time of initial progression should be used as the reference baseline for comparison with the post-progression assessment.
- New lesions are considered measurable at the time of initial progression if the long axis is more than 15 mm regardless of the short axis. If a lymph node has a long axis of 11 to 15 mm, it should only be considered measurable if its short axis is more than 10 mm.
- Any new lesion considered non-measurable at the time of or after initial progression may become measurable and therefore included in the tumor burden determination.

4.3.8.4 Radiographic assessment for subjects who discontinue study drug during post-progression treatment

For subjects that discontinue post-progression treatment, no additional radiographic assessments will be required. Upon treatment discontinuation, these subjects will continue in the follow-up phase of the study (see [section 5.1](#)). Subjects who proceed to allogeneic SCT or ASCT will be followed as described in [Section 5.4](#).

4.4 Blinding/Unblinding

Not applicable.

4.5 Treatment Compliance

Treatment compliance will be monitored by drug accountability as well as the subject's medical record and eCRF.

4.6 Destruction and Return of Study Drug

4.6.1 Destruction of Study Drug

For this study, study drugs (those supplied by BMS or sourced by the investigator) such as partially used study drug containers, vials and syringes may be destroyed on site.

Any unused study drugs can only be destroyed after being inspected and reconciled by the responsible BMS Study Monitor unless study drug containers must be immediately destroyed as required for safety, or to meet local regulations (eg, cytotoxics or biologics).

On-site destruction is allowed provided the following minimal standards are met:

- On-site disposal practices must not expose humans to risks from the drug.
- On-site disposal practices and procedures are in agreement with applicable laws and regulations, including any special requirements for controlled or hazardous substances.
- Written procedures for on-site disposal are available and followed. The procedures must be filed with the site's SOPs and a copy provided to BMS upon request.
- Records are maintained that allow for traceability of each container, including the date disposed of, quantity disposed, and identification of the person disposing the containers. The method of disposal, ie, incinerator, licensed sanitary landfill, or licensed waste disposal vendor must be documented.
- Accountability and disposal records are complete, up-to-date, and available for the Monitor to review throughout the clinical trial period.

If conditions for destruction cannot be met the responsible BMS Study Monitor will make arrangements for return of study drug.

It is the investigator's responsibility to arrange for disposal of all empty containers, provided that procedures for proper disposal have been established according to applicable federal, state, local, and institutional guidelines and procedures, and provided that appropriate records of disposal are kept.

4.6.2 Return of Study Drug

If study drug will not be destroyed upon completion or termination of the study, all unused and/or partially used study drug that was supplied by BMS must be returned to BMS. The return of study drug will be arranged by the responsible BMS Study Monitor.

It is the investigator's responsibility to arrange for disposal of all empty containers, provided that procedures for proper disposal have been established according to applicable federal, state, local, and institutional guidelines and procedures, and provided that appropriate records of disposal are kept.

